- To compare the clinical safety and tolerability of CBP-307 with those of placebo administered for 12 weeks in subjects with moderate to severe UC
- Incidence, type and severity of TEAEs and SAEs as well as their relations with the investigational product, AEs and SAEs that lead to discontinuation of study, and AEs of special interest (cardiac events as well as pulmonary function tests, ophthalmologic examinations skin examinations, and nervous system physical examinations); AEs will be graded according to CTCAE version 5.0 in the study stage 1
- 12-lead ECG findings, abnormal clinical laboratory tests (the hematology test, blood chemistry test, urinallysis and coagulation test), vital signs and results of physical examination

Exploratory

- To evaluate the PK/PD of CBP-307 orally administered in subjects with moderate to severe UC in study stage 1
- To evaluate IBDQ in study stage 1 and stage 2
- To evaluate the safety and tolerability of CBP-307 after medium or long-term administration (in study stage 2) in subjects with moderate to severe UC
- To evaluate clinical remission, clinical response and mucosal healing in subjects with moderately to severely active UC who respond after 12 weeks of induction therapy in the stage 1 study, thereby to evaluate the efficacy of CBP-307 orally administered for maintenance treatment compared with placebo in sub-study 1 of the study stage 2
- To evaluate clinical remission, clinical response and mucosal healing in

- Plasma concentration of CBP-307 in subjects with moderate to severe UC
- Absolute lymphocyte count
- Total Igs (IgA, IgG and IgM)
- C-reactive protein (CRP) as a biomarker of plasma protein
- Fecal calprotectin as a fecal biomarker to be analyzed
- Change from baseline in IBDQ total score and subscore at week 12 after treatment (in the study stage 1), at week 24, and week 48 (in the study stage 2)
- Incidence, type and severity of TEAEs and SAEs as well as their relations with the investigational product, AEs and SAEs that lead to discontinuation of study, and AEs of special interest (cardiac events as well as pulmonary function tests, ophthalmologic examinations, skin examinations, and nervous system physical examinations); AEs will be graded according to CTCAE version 5.0 in study stage 2
- Change in 12-lead ECG findings, abnormal clinical laboratory tests (the hematology test, blood chemistry test, urinalysis and coagulation test), vital signs and results of physical examination in the study stage 2

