7.5. Monitoring of adverse events of special interest

During the study on CBP-307, AEs caused by S1P1 receptor stimulation that were found in previous clinical studies on other similar drugs will be closely monitored. These AEs include:

- a. Bradycardia and cardiac conduction abnormalities: It was reported that the adverse reactions caused by the first dose of similar drugs mainly included reversible bradycardia, first grade atrioventricular block and sinus arrest. Reduced heart rate is an expected adverse reaction to S1P1 agonists. These negative chronotropic effects of S1P1R agonists appear to attenuate over time after S1PR desensitization and internalization into cardiac myocytes. This effect appears to occur with increasing exposure to study drug; thus, gradual titration of the dose of CBP-307 within 1 week may mitigate against larger reductions in heart rate.
- b. Pulmonary toxicity: An initial sharp decrease followed by slow progressive decline over time in FEV₁ was observed in clinical studies of the same category of drugs. In this study, FEV₁ and FVC in all subjects will be measured; DLCO will be measured in sites that are equipped with the right facilities. Each subject with abnormal pulmonary function test results will be followed up. If the subject's pulmonary function test results (FEV₁ and/or FVC) fall below 50% of the predicted values, treatment should be discontinued immediately, and appropriate clinical follow-up (for at least 3 months) should be performed until the resolution is confirmed or no further aggravation is expected by investigator.
- c. Hepatotoxicity: fingolimod caused frequent, reversible liver enzyme elevations greater than 3-fold above the ULN in up to 12% of patients. In the completed phase I clinical study on CBP-307, ALT levels slightly increased in individual subjects but were all below 3 times the ULN; and this side effect was also milder than that of fingolimod. In this study, blood chemistry analysis will include measurement of LFT levels. Subjects with abnormal LFT levels will be continuously followed up until the LFT values returns to the normal/baseline level.

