- d. Macular edema: In the preclinical and clinical phase I studies of CBP-307, no eye-related toxicity was observed yet. In this trial, OCT examination will be included. Subjects with macular edema must discontinue the investigational product and undergo examinations including a dilated fundus examination. Every subject whose ophthalmic evaluations reveal abnormalities will be followed until values return to baseline.
- e. Opportunistic infection or severe infection: Tuberculosis, serious bacterial infections, systemic fungal infections, viral infections such as herpes infections (including herpes

- zoster and disseminated herpes simplex) and protozoal infections during the study should be reported as AESI.
- f. Basal cell carcinoma: In a 2-year placebo-controlled clinical study on fingolimod (a similar drug), the incidences of basal cell carcinoma are 2.0% in the group treated with fingolimod 0.5 mg and 0.1% in the placebo control group, respectively. Subjects should be observed for suspected skin lesions, and a specialist assessment should be performed immediately if any suspected skin lesions are noted.
- g. Posterior reversible encephalopathy syndrome and progressive multifocal leukoencephalopathy.

The following steps should be followed:

- a. At every visit, vital signs should be measured in the supine position.
- b. Subjects will be closely monitored in the clinic after their first dose of the initial dose titration regimen for a period of 6 hours after administration. ECGs will be performed predose and at 4 and 6 hours after drug administration, with more frequent assessments as clinically indicated. Vital signs will be measured before administration and at every hour in 6 hours after administration. During titration period, continuous overnight cardiac monitoring should be performed in patients who experience symptomatic bradycardia that requires pharmacologic intervention. In these patients, the first-dose monitoring strategy will continue the following days until the symptoms improve by investigator's assessment, even if the study drug is discontinued. If anyone has prolonged QTc interval during 6-hour observation after dosing, repeated cardiac monitoring in the following days will be conducted until the abnormity improves.

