8.1. Adverse event

8.1.1. Definition and recording of adverse events

Definition: An adverse event refers to any untoward medical occurrence that occurs after the subjects signs the ICF, which does not necessarily have a causal relationship with the investigational product. Thus, an AE can be any unfavorable and unintended symptom, sign, disease or condition, or an abnormal test finding, whether or not it is related to the investigational product. AEs include:

- Symptoms described by the subject, or signs observed by the investigator, and
- Abnormal findings (involving laboratory tests, ECG, and an X-ray) that result in changes in medical care (diagnostic or therapeutic).
- Exacerbation of chronic or intermittent pre-existing diseases, including increased incidence and/or diseases severity.

An abnormality found at screening visit is not an AE unless it has reappeared after disappearance or is worsened during the trial.

Note: Regarding a heart rate decrease (bradycardia) and decreased lymphocyte count in peripheral blood in this study, please report them as follows:

- Since a decreased lymphocyte count in peripheral blood is due to the mechanism of action of the drug, it itself is not to be reported as an AE. However, clinical diagnosis related to a decreased lymphocyte count in peripheral blood indicates AE reporting (if no diagnosis is available, it is required to report related clinical symptoms or signs).
- The heart rate decrease (bradycardia) in this study is defined as a heart rate of <50 beats per minute in the awake state or a heart rate of ≥50 beats per minute in the awake state whereas subjects experience clinical symptoms due to a reduced heart rate (if subjects have a heart rate <50 beats per minute in the awake state and need clinical treatment, such condition is considered a grade II AE).

In this study, AE data will be collected after subjects sign informed consent forms, and AEs will be persistently monitored throughout the study, i.e., until 28 days after the last dose.

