8.3. Reporting of adverse events of special interest

In a phase I clinical study on CBP-307 conducted in Australia, potential risk for cardiovascular events was observed in the high-dose group (treated with a dose more than 10 times the therapeutic dose to be administered in this study). Besides, in the post marketing studies of the marketed S1P1 agonist fingolimod and other clinical studies of S1P1 agonists, other potential safety risks were also observed, including pulmonary toxicity, hepatotoxicity, macular edema, severe and opportunistic infections, and skin tumors. Although these potential risks were not observed in the phase I clinical study of CBP-307, special attention is still needed in this study. AEs that require special attention include (see Section 7.5 for detail):

- a. bradycardia and cardiac conduction abnormalities: significant bradycardia (heart rate ≤ 45 beats/min), Mobitz type II or third degree atrioventricular block, and other significant cardiac conduction abnormalities,
- b. pulmonary toxicity: difficulty in breathing and clinically significant wheezing, and
- c. hepatotoxicity: e.g., two consecutive liver function tests in a subject suggesting elevated liver enzymes, AST or ALT > 3 times the ULN, or other clinically significant liver dysfunction.
- d. Macular edema
- e. Opportunistic infection or severe infection: tuberculosis, serious bacterial infections, systemic fungal infections, viral infections such as herpes infections (including herpes zoster and disseminated herpes simplex) and protozoal infections.
- f. Malignant neoplasm of skin

All AEs of special interest specified in the protocol (see Section 7.5) have to be reported to sponsor and CRO, regardless of seriousness and relationship to the investigational product.

- For events conforming to the requirements of SAE, report according to expedited reporting procedures for SAE (see Section 8.2);
- Regarding an event that does not meet the criteria for a SAE, it is only needed to be recorded in the eCRF.

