15.1.5. ADVERSE EVENTS OF SPECIAL INTEREST

Adverse events of special interest are those events which are recorded as "Yes" to the item "Is This an Adverse Event of Special Interest?" on the Adverse Events page of the eCRF. The adverse event of special interest will include the following:

- Bradycardia and cardiac conduction abnormalities
- Pulmonary toxicity
- Hepatotoxicity
- Macular Edema
- Opportunistic or serious infections
- Malignant neoplasm of skin
- Posterior reversible encephalopathy syndrome
- Progressive multifocal leukoencephalopathy.

A summary of adverse event of special interest by SOC and PT will be presented.

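### The protocol describes the pulmonary, skin and bradycardia events of special interest inconsistently, and the SAP counts only events the site ticked, so this part of the secondary safety endpoint depends on which section a site applied

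*Protocol*

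**What the plan says.** The stage 1 secondary safety endpoint in the protocol synopsis includes "AEs of special interest (cardiac events as well as pulmonary function tests, ophthalmologic examinations skin examinations, and nervous system physical examinations". Section 4 repeats this and specifies that the lung function tests are abnormal ones.

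Section 7.5 lists seven lettered items. The cardiac item has no heart-rate cut-off; it says that first-dose reactions to similar drugs "mainly included reversible bradycardia, first grade atrioventricular block and sinus arrest". The pulmonary item is written around FEV1, FVC and DLCO. The skin item begins "Basal cell carcinoma: In a 2-year placebo-controlled clinical study on fingolimod". The last item is "Posterior reversible encephalopathy syndrome and progressive multifocal leukoencephalopathy".

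Section 8.3, which governs reporting, lists six items. Its cardiac item is "significant bradycardia (heart rate ≤ 45 beats/min), Mobitz type II or third degree atrioventricular block", plus other significant conduction abnormalities. Its pulmonary item is "pulmonary toxicity: difficulty in breathing and clinically significant wheezing". Its skin item is any malignant skin neoplasm. The section refers to 7.5 twice, once for detail and once for what must be reported. An AESI that is not serious need only be entered in the eCRF.

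Section 8.1.1 defines the bradycardia adverse event as "a heart rate of <50 beats per minute in the awake state", or a higher rate with symptoms.

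SAP 15.1.5 states "Adverse events of special interest are those events which are recorded as" Yes on the eCRF AESI question. It names eight categories, without thresholds or a preferred-term list, and summarizes by system organ class and preferred term.

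**The concern.** An AESI table is useful only if the same clinical event is classified the same way at every site and in both arms. Here the classification is left to a tick box, and the sections a site would consult when answering it do not agree. The SAP adds no rule of its own: it neither fixes thresholds nor derives AESIs from the laboratory, ECG, vital-sign or lung function data. Two subjects with identical findings could be counted differently, and a reader of the table could not tell which definition was applied. For a drug class whose cardiac and pulmonary effects are the reason for naming AESIs at all, those are the categories where the count should be cleanest.

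**Working it through.** There is no planned figure to reproduce, so the check is a comparison of definitions.

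**1. Length of the lists.** Protocol 3.5 names eight conditions. Section 7.5 has seven lettered items covering eight conditions, because the last item holds two. Section 8.3 has six. SAP 15.1.5 has eight.

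**2. The items that differ.**

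| Item | 7.5 | 8.3 | Elsewhere |
|---|---|---|---|
| Pulmonary | lung function tests | symptoms only | endpoint wording: lung function tests; SAP: heading only |
| Skin | basal cell carcinoma | any skin malignancy | 3.5: skin tumors; SAP: as 8.3 |
| Bradycardia | no cut-off | ≤ 45 beats/min | 8.1.1: < 50 awake, as an AE; SAP: heading only |
| PRES and PML | listed | not listed | 3.5 and SAP: listed |

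**3. Events whose status changes with the section read.**
- Awake heart rate of 46 to 49 without symptoms: an adverse event under 8.1.1, bradycardia without a limit under 7.5, outside the numeric criterion in 8.3.
- First-degree AV block: mentioned in 7.5, not named in 8.3.
- Fall in FEV1 or FVC without symptoms: within 7.5 and the endpoint wording, outside the 8.3 item.
- Breathlessness or wheeze with normal lung function: within 8.3, outside the 7.5 item.
- Skin malignancy other than basal cell carcinoma: within 8.3 and the SAP, outside the 7.5 item.

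**4. Does the cross-reference from 8.3 to 7.5 settle it?** For PRES and PML, yes: 8.3 makes the AESIs specified in 7.5 reportable. For bradycardia, no: 7.5 has no number. For skin, no: 7.5 is the narrower text. For pulmonary events, only in part: it leads the reader to lung function, but the value given there, 50% of predicted, is a rule for stopping treatment (also in 5.4.4), not a stated AESI threshold.

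**5. Do other SAP tables count the same subjects?**
- Liver tests: SAP 15.3 counts subjects at multiples of ULN from 3 upward, whatever was ticked.
- Heart rate: SAP 15.5 flags a value ≤ 50 together with a fall of at least 15. A subject going from 58 to 45 falls by 58 − 45 = 13, so meets the 8.3 figure but not the SAP flag. A subject going from 65 to 50 falls by 15 and is flagged, but meets neither 8.3 nor the 8.1.1 rate criterion.
- Lung function: SAP 15.7.1 gives values and changes by visit, with no count of subjects below 50% of predicted. Under SAP 6.3, unscheduled measurements do not enter by-visit summaries.
- Holter: listed only (SAP 15.4).

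No planned table therefore counts subjects at ≤ 45 beats/min or below 50% of predicted FEV1 or FVC.

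**6. Size.** With 52 planned subjects per arm, one reclassified subject moves that arm's rate by 1/52 = 0.0192, or 1.9 percentage points. How many would be reclassified cannot be computed: the documents give no AESI rates for this trial.

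**The case against.** The best defence is that 8.3 is not meant to stand alone. Its list is introduced as inclusive, sends the reader to 7.5 for detail, and attaches the reporting duty to the events specified in 7.5. A reader might infer from the 8.3 list that a PRES or PML case could go unreported as an AESI. The documents do not support that: the cross-reference covers both, and Section 3.5 and SAP 15.1.5 name both. The missing entry is a minor drafting gap.

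A reader might also infer that the gravest events could disappear from the report. They would not. An unticked event that is treatment-emergent stays in the TEAE tables and, where applicable, in the serious and discontinuation tables (SAP 15.1.1 to 15.1.3). Liver tests, ECG, vital signs and lung function are summarized from measured data. Safety is descriptive, with no comparisons tested (SAP 15).

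Nor do the documents show that sites did classify differently. The eCRF completion instructions are not among them, and Section 8.1.2 sends ongoing safety data to a medical monitor, so the tick may not have been the only control.

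Finally, it is tempting to say that AESI counts will be so small that one event decides the reading. The class rates in 7.5 are for fingolimod, not for this drug, and no decision rule depends on the AESI table.

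All of this limits the consequence. It does not reconcile the pulmonary, skin and bradycardia wording, and it does not give the SAP a definition that can be applied the same way twice.

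**Conclusion.** The inconsistency is real for three items: pulmonary toxicity, skin malignancy and bradycardia. Because SAP 15.1.5 relies on the site's tick alone, the AESI component of a stated secondary safety endpoint depends on which section the site applied. The effect is confined to that descriptive component: 1.9 percentage points per reclassified subject, assuming 52 per arm as planned, with the number of such subjects unknown. Alpha, power and the primary result are untouched. The conclusion assumes that no eCRF guidance or central review outside these documents already imposes a single definition; if one exists, the SAP should cite it. The point is worth acting on because the remedy is cheap and uses data already collected.

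**What to change.** Reconcile Protocol 3.5, 7.5, 8.3, the endpoint wording (synopsis and Section 4) and SAP 15.1.5 into one AESI definition covering the eight SAP categories, and state how it relates to the bradycardia definition in 8.1.1. The clinical content, including every threshold, is for the sponsor to choose. In particular, the 50%-of-predicted stopping rule should not become an AESI threshold by default.

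In SAP 15.1.5, keep the site tick and add a programmed flag that applies the reconciled criteria to the adverse event, vital-sign, ECG, liver test and lung function data already held. Use prespecified preferred terms for each category, and state which heart-rate recordings count if the criterion refers to the awake state. Tabulate ticked and derived AESIs side by side by category.

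The programming cost is small, and AESI counts may rise slightly. Changing the protocol text would need ethics committee approval (Section 2.1). The protocol planned to finish in September 2022 and the SAP is dated January 2023; if collection ended as planned, new protocol wording cannot alter what sites ticked, and the derived flag carries most of the benefit.

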8.4. Follow up of subjects with adverse events/serious adverse events

The investigator should closely monitor every subject experiencing an AE, including monitoring the clinical changes in the subjects. The investigator needs to proactively follow up each subject and provide sponsor and CRO with more detailed information about AE/SAE. During the study, all AEs/SAEs should be followed up until resolved, stabilized or returned to baseline status, unless the investigator believes that given the subject's underlying condition, there is little hope that the AEs/SAEs will be resolved.

8.5. Handling of abnormal laboratory test results

If the laboratory test data is abnormal and cannot be explained, the test should be repeated immediately. If retest confirms that a result is abnormal and clinically significant, it should be recorded as an AE (except a decreased lymphocyte count, see Section 8.1 for details).

8.6. Clinical laboratory parameters and abnormal laboratory test results

Regarding major abnormal changes in laboratory parameters, which are judged by the investigator to be clinically significant, they will be recorded as AEs (except a decreased lymphocyte count, see section 8.1.1 for details).

During treatment, both the total white blood cell count and the white blood cell classification data is blinded.

If any of the following results are observed, the investigator will need to repeat the test:

- Absolute lymphocyte count $< 0.2 \times 10^9/L$
- Absolute neutrophil count $< 1.0 \times 10^{9}/L$
- Total white blood cell count $> 20 \times 10^{9}/L$

If the value of the repeated test also exceeds the above numerical limit, the investigator should be informed of the abnormal results of the subject.

If the absolute lymphocyte count or total white blood cell count is determined to be below an acceptable threshold, the medical monitor will contact the investigator responsible for treatment to ask him/her to closely monitor the event that may lead to serious infection and to follow up the subject appropriately.

If the absolute lymphocyte count is $< 0.2 \times 10^{9}$ /L, the subject should temporarily discontinue the investigational product. The absolute lymphocyte count should be retested every 3 days. If the retest result shows that the lymphocyte count rises to $> 0.5 \times 10^{9}$ /L, the investigator will be informed that the value is within the acceptable range, and the investigational product can be restarted (the statement of investigational product restart after interruption is shown in Section 6.2). If the lymphocyte count could not return to at least 0.5×10^{9} /L after 2 weeks, the investigator should discuss with sponsor and the medical director of CRO whether subjects can continue participating in the study.

Bradycardia

The results of the completed phase I clinical trial showed that at clinically relevant dose levels, heart rate decrease was observed on the first two days of single and multiple dosing. This effect on heart rate was observed in other S1P1 modulators. Given that this is due to the mechanism of action of the drug, the AE of heart rate decrease (bradycardia) in this study is defined as a heart rate of <50 beats per minute in the awake state or a heart rate of ≥50 beats per minute in the awake state whereas subjects experience clinical symptoms due to a reduced heart rate (if subjects have a heart rate <50 beats per minute in the awake state and need clinical treatment, such condition is considered a grade II AE). In the completed Australian Phase I clinical study, it was defined that a heart rate of <45 beats per minute in the awake state was required to be reported as an AE, and this adverse event does not serve as a criterion for termination of the trial/treatment.

Reduction of peripheral blood lymphocyte count

The results of the completed Australian Phase I clinical trial indicate that at clinically relevant dose levels, the drug may reduce the peripheral blood lymphocyte count, which is the efficacy indicator of the drug. It itself is not to be reported as an AE. However, clinical diagnosis related to a decreased lymphocyte count in peripheral blood indicates AE reporting (if no diagnosis is available, it is required to report related clinical symptoms or signs).

Reduction of peripheral blood lymphocyte count

A reduction in the peripheral blood lymphocyte count directly leads to a reduction in the WBC count.

Note: In this study, heart rate decrease (bradycardia), a reduction in the peripheral blood lymphocyte count and a reduction in the peripheral WBC count (a reduction in the peripheral blood lymphocyte count directly leads to a reduction in the WBC count) are not considered as criteria for termination of the trial/treatment.

